7.5.2 ORR by Investigator

The ORR per RECIST 1.1 by investigator will be analyzed as described in Section 7.5.1 above, respectively. Only 95% confidence levels will be used in these exploratory analyses. The P-ITT and ITT populations will be used.

7.5.3 Time to Progression (TTP)

Time to progression is defined as the time from randomization until tumor progression per RECIST v1.1. Subjects who die due to progressive disease will be considered as events and those who die for other reasons will be censored on the day they died.

$$\text{Time to progression (months)} = (\text{earliest date of radiographic progressive disease or death due to progressive disease or censoring} - \text{date of randomization} + 1)/30.4375$$

The TTP will be analyzed separately for radiographic tumor assessments per BIRC and per Investigator for both PITT and ITT populations. For TTP, the dates of progression and censoring per BIRC are shown in column PFS-EP-1 and PFS-EP-3 of Table 8 respectively. However, only deaths due to progressive diseases will be considered as events and those due to other reasons will be censored at the date of death.

Time to progression will be analyzed using the same analysis methods (Kaplan-Meier and Cox proportional hazards model) as for the analysis on PFS (see Section 7.1.1.6).

7.5.4 Duration of Objective Response (DOR)

Duration of objective response is defined as the time from the first documentation of objective response that is subsequently confirmed at a visit that is ≥ 28 days later to disease progression or death due to any cause.

$$\text{Duration of response (months)} = (\text{earliest date of progressive disease or death due to any cause or censoring} - \text{date of first objective response} + 1)/30.4375$$

Duration of objective response will be computed only among subjects who experience an objective response (confirmed CR or confirmed PR). DOR will be computed both by BIRC and by Investigator and analyzed separately. For DOR per BIRC and per Investigator, the dates of progression and censoring are shown in column PFS-EP-1 and PFS-EP-3 of Table 8, respectively.

Duration of objective response will be analyzed using the same analysis method (Kaplan-Meier) as for the analysis on PFS (see Section 7.1.1.6) for both P-ITT and ITT populations.

7.5.5 PFS and ORR per modified RECIST (mRECIST)

The analysis of PFS and ORR per BIRC using modified RECIST (Lencioni, 2010) criteria will be as described in Sections 7.1.1.3 and 7.4 above, respectively. Modified RECIST measurements will be derived computationally from reader-approved target lesion contours and subjective non-target lesion assessments by the BIRC based upon standard CT/MRI images obtained for the RECIST 1.1 assessments. Only 95% confidence levels will be used in these exploratory analyses. Summary tables will be provided for both the PITT and ITT population.

7.5.6 Pharmacokinetics (PK)

Blood samples will be obtained from all subjects in the experimental arm (cabozantinib + atezolizumab) and the single-agent cabozantinib arm for cabozantinib concentration measurements. Blood samples will be obtained from all subjects in the experimental arm for atezolizumab concentration measurement. Pharmacokinetics analyses of cabozantinib and atezolizumab are outside the scope of this plan. A separate PK analysis plan and PK report will be provided. In addition, population PK and exposure-response analyses of cabozantinib will be explored and reported separately. PK analyses will also be conducted among the subset of subjects enrolled in China.

7.5.7 Immunogenicity Assessments

This is beyond the scope of this plan.

7.5.8 Serum Alpha-Fetoprotein (AFP)

Serum AFP is assessed in the study at various time points such as baseline, W4D1, W7D1, W10D1, W13D1, FU1, and FU2. Serum AFP will be analyzed as a continuous and discrete variable (<400 ng/mL, ≥ 400 ng/mL) to assess its potential as a prognostic marker. The serum levels and change from baseline (absolute and percent change) will be summarized using descriptive statistics at various measurement time points and presented by study treatment arm for both PITT and ITT populations. Descriptive statistics for best/worst percent change since baseline will also be presented per arm using all available data at protocol-defined time points.

Best change is defined as the largest reduction (or smallest increase if no reduction) and worst change is defined as the largest increase (or smallest reduction if no increase).

Appropriate transformations may be applied to normalize the data for presentation or analysis. AFP may also be categorized based on previously published measures. For example, a decrease from baseline of 20% or more in serum AFP by or at a specific time point (say, W7D1) may be defined post-hoc as a prognostic response.

Exploratory modeling analyses including survival analyses with time dependent covariates, general linear models, and mixed models with repeated measures will be employed to assess meaningful relationships between AFP levels or changes from baseline and clinical outcomes.

A waterfall plot of best percentage change (i.e., best percentage decrease) from baseline in AFP will be presented for each treatment group using the PITT and ITT populations. In all calculations, best change from baseline will be based only on protocol-defined time-points.

7.5.9 Peripheral Biomarkers

The tumor PD-L1 status will be used for subgroup analysis as discussed in Section 7.6.

Additional peripheral biomarker analysis is outside the scope of this plan.

7.5.10 Health-Related Quality of Life (HRQOL)

Health-related quality of life (HRQOL) will be assessed by the EuroQol Health questionnaire instrument (EQ-5D-5L) (Reenen MV, 2019). The questionnaire will be self-completed by the subjects at various time points until disease progression and will provide a generic measure of health for clinical appraisal (see protocol Section 5.7.7). The EQ-5D-5L questionnaire has two pages: a descriptive page which assesses on an increasing severity scale of 1-5 changes in the following five questions (dimensions): mobility, self-care, usual activities, pain/discomfort, and anxiety/depression. The second page has a 0-100 visual analogue scale (VAS) which records the subjects self-rated health between 100 (best health you can imagine) and 0 (worst health you can imagine) and serves as quantitative measure of health by the subject (see protocol Appendix D and EQ-5D-5L User Guide 2019).

To compare each of the cabozantinib containing arms with sorafenib, the following summaries are planned at each time point for each of the 6 questions for PITT and ITT populations:

Within each treatment arm:

- Descriptive statistics (number of observations, mean and standard deviation)
- Rate of completion for the questionnaire at each time point. This is defined as total number of subjects who answered all questions on the EQ-5D-5L questionnaire / the expected total number of subjects still on study at the visit

- Mean change from baseline at each time point and the corresponding 95% CI and p-value from one-sample t-test
- Effect size for change from baseline within arm, calculated as (mean of change in score/pooled standard deviation for baseline scores). An effect size greater than ≥ 0.3 will be considered potentially clinically meaningful
- Shift in the severity scale since baseline

Across treatment arms

- The difference in the effect sizes will be presented
- Difference in mean change from baseline for the questions at the time point will be evaluated by a two-sample t-test
- Line plots for mean \pm standard error and the corresponding mean for change from baseline over time. Data from all treatment arms will be displayed on the same plot. In addition, these plots will also show the average state of the subjects at 3 landmark points, namely, around end of treatment, around progression and around 30 days post treatment follow-up for the two treatment arms
- Percentage of subjects in Level 1 (no problem) vs. Levels 2-5 (any problems) will be summarized over time
- Percentage of subjects with any problems (Level 2-5) will be compared between the treatment arms using a bar chart

The EQ-5D-5L may be converted into a single index (EQ-Index) value normalized across different countries where the index is validated. See Appendix D for conversion details. For EQ-VAS and EQ-Index, descriptive statistics for change from baseline at each time will be presented. Plots for mean \pm standard error and mean change from baseline \pm standard error over all time points for the two treatment arms will be generated. In addition, repeated-measures mixed-effects models will be used to explore treatment differences over time. These analyses will include the outcome variable of QOL score change from baseline. The predictors (fixed effects) will be the baseline scores, treatment arms, visit, and randomization strata described in Section 2.4. The individual subject nested within the planned treatment arm will be the random effect. All available data will be included for the analysis. The estimated least squares means for the two treatment arm and their difference, the p-values comparing the 2 treatment arms and the effect size will be presented. No adjustment will be made for multiple comparisons. An effect size of difference ≥ 0.3 will be considered potentially clinically meaningful.

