5.8.8. Health-related Quality of Life Assessments

Health-related QOL assessments will be performed using the EuroQol Health questionnaire instruments EQ-5D-5L ([Appendix L](#)). This is a standardized instrument for use as a measure of self-reported general health status. The EQ-5D-5L comprises 5 dimensions (mobility, self-care, usual activities, pain/discomfort, and anxiety) and a visual analog scale (VAS). The utility data generated from EQ-5D-5L are recommended for and commonly used in cost effectiveness analysis. The first assessment will be performed within 14 days prior to randomization.

Assessment will be collected every 6 weeks after W1D1 (eg, W7D1, W13D1, etc). For randomized subjects who never receive study treatment, W1D1 is defined as the date of randomization. Subjects will continue completing questionnaires regardless of whether study treatment is given, reduced, held, or discontinued until the date of the last tumor imaging assessment or the study meets its primary endpoints. Consequently these assessments may be required in the Post-Treatment Period for some subjects ([Appendix A](#)).

Subjects are to complete the questionnaires prior to each clinic visit or, if completed on the day of the visit, before seeing the study site personnel. If a clinic visit is not possible subjects should complete the questionnaires as per schedule and return it to the site either during the next visit or should send it to the site by fax or postal mail. Ideally, study subjects should not receive any information about their most recent medical results prior to completing the questionnaires in order to ensure that their reporting is not influenced by such information when completing the questionnaires. At clinic visits, questionnaires should be carefully reviewed by the study staff at the site for completeness.

Subjects who are not compliant with completing the questionnaires should be reminded by the Investigator that these reports are an essential part of the study and timely completion is required.

Every effort should be made by the study site to retrieve all HRQOL questionnaires including the assessment following radiographic progression or discontinuation of study treatment, and to keep them at the site as source documentation.

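### The EQ-VAS and EQ-Index mixed model has no treatment-by-visit term, so it reports one constant arm difference, weighted to early visits by attrition

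*SAP*

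**What the plan says.** SAP 7.5.10 gives the purpose of the model for EQ-VAS and EQ-Index: "repeated-measures mixed-effects models will be used to explore treatment differences over time". The outcome is change from baseline. On the fixed effects it says: "The predictors (fixed effects) will be the baseline scores, treatment arms, visit, and randomization strata described in Section 2.4". On the random part: "The individual subject nested within the planned treatment arm will be the random effect". On the data: "All available data will be included for the analysis". The output is a single contrast, "The estimated least squares means for the two treatment arm and their difference", with a p-value and an effect size, and the section adds: "An effect size of difference ≥ 0.3 will be considered potentially clinically meaningful".

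Outside the model, the same section plans comparisons at each time point for six questions, that is, the five dimensions and the VAS. The difference in mean change from baseline "for the questions at the time point will be evaluated by a two-sample t-test". It also plans by-visit means, changes, shift tables and line plots. For EQ-VAS and EQ-Index it adds descriptive statistics and plots by visit.

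On timing, Protocol 5.8.8 says: "Assessment will be collected every 6 weeks after W1D1 (eg, W7D1, W13D1, etc". Collection runs until the last tumor imaging or until the study meets its primary endpoints. Protocol 5.8.6.2 continues imaging until both investigator-assessed progression and permanent treatment discontinuation have occurred. SAP 7.5.10 describes collection as lasting until progression. SAP 7.5 treats exploratory endpoints as supportive and unadjusted for multiplicity.

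**The concern.** A model with main effects for arm and visit fits parallel profiles. Visit moves both arms together, and arm shifts one profile by a constant. A random intercept per subject does not change this. The model therefore cannot display a difference that emerges, fades or reverses, although that is its stated purpose.

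When the true difference is not constant, the arm coefficient is a weighted average of the visit-specific differences. The weights follow from how many subjects remain and how strongly their scores are correlated. The plan does not choose them. Since questionnaires end around progression or treatment stop, later visits hold fewer subjects and count for less. The resulting number is then given a p-value and compared with 0.3. The conclusion about quality of life could turn on weights that nobody specified.

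**Working it through.** **The plan's own figures.** The documents give no power or effect figure for this model, so there is none to reproduce. The PFS medians borrowed below are internally consistent: 3.6/6.0 = 0.60, the stated HR. Schoenfeld's formula with 2:1 allocation gives (2.576 + 1.282)² / [(2/3)(1/3)(ln 0.6)²] = 14.88/0.0580 ≈ 257 events, as stated in SAP 2.3.

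**Inputs from the documents.** Arm sizes 370 and 185, exponential PFS with medians 6.0 and 3.6 months (SAP 2.3), and a visit every 6 weeks (Protocol 5.8.8), which gives eight visits from W7 to W49.

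**Assumptions not in the documents.** Questionnaires stop at the PFS time, and within-subject correlation ρ is 0 to 0.7. Baseline and strata are left out of the calculation because they do not create a time-varying arm effect.

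**Step 1: retention.** n(t) = n₀ × 0.5^(t/median). At W7, t = 42/30.4375 = 1.38 months.
- Combination: 370 × 0.5^(1.38/6.0) = 315 at W7, falling to 103 at W49.
- Sorafenib: 185 × 0.5^(1.38/3.6) = 142 at W7, falling to 22 at W49.

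**Step 2: weights.** Under generalised least squares for arm + visit with a random intercept, the arm coefficient equals Σ wⱼδⱼ, where δⱼ is the true difference at visit j and Σ wⱼ = 1. At ρ = 0, wⱼ is proportional to n₁ⱼn₂ⱼ/(n₁ⱼ + n₂ⱼ). From W7 to W49 these terms are 97.8, 77.4, 61.1, 48.2, 37.9, 29.7, 23.3 and 18.2, which sum to 393.6. The first four sum to 284.5, and 284.5/393.6 = 72%. Higher ρ moves more weight to the early visits:

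| Retention scenario | First four visits, ρ = 0 to 0.7 |
|---|---|
| Plan's medians, 6.0 v 3.6 | 72% to 83% |
| Single-agent cabozantinib v sorafenib, 5.5 v 3.6 | 71% to 82% |
| Both arms 3.6 | 74% to 85% |
| Both arms 6.0 | 65% to 76% |
| No dropout | 50% (0.125 per visit) |

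Under the plan's medians W7 alone carries 0.25 to 0.39, and W49 carries 0.03 to 0.05.

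**Step 3: effect on the 0.3 threshold.** Take δⱼ = 0.6 × j/8 SD. The equal-weight average is 0.6 × 4.5/8 = 0.34. The model's Σ wⱼδⱼ is 0.25 at ρ = 0 and 0.20 at ρ = 0.7, so the threshold verdict changes.

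**Step 4: a reversal.** Take +0.3 at the first four visits and −0.3 at the last four, averaging 0. The model gives 0.3 × (2 × 0.723 − 1) = 0.13 at ρ = 0 and 0.3 × (2 × 0.831 − 1) = 0.20 at ρ = 0.7. Its output shows no sign of the change in direction.

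**The case against.** The strongest reply is that the section as a whole does show time patterns. It has between-arm t-tests at each visit for the five items and the VAS, with descriptives, plots and landmark displays. An early loss followed by recovery would be visible there. That stands, and it confines the point to the model. It does not remove the point. The t-tests are unadjusted, observed-case comparisons. EQ-Index, if derived, has no by-visit test. The only adjusted analysis using all visits is the one that cannot vary over time.

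A second reply is that PFS is a harsh proxy for retention. This also stands. Treatment beyond progression is allowed and imaging continues with it, so questionnaires may last longer and the early weighting would lessen.

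A third is that an information-weighted average is a legitimate summary and that the endpoint is supportive. Both are fair. But the plan never chooses that average, and it sets a p-value and a relevance threshold against it.

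Three stronger readings are tempting, and the documents do not support them:
- A reader might infer that unequal dropout between arms causes the early weighting. Equal dropout produces much the same weights, so attrition itself is the cause.
- A reader might infer that the t-tests ignore baseline. They compare change from baseline.
- A reader might infer that the item-level t-tests must be replaced by ordinal or covariate-adjusted models. That is a preference on a supportive endpoint, and the section already has severity shifts and a no-problem versus any-problem summary.

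**Conclusion.** The point holds for the model-based EQ-VAS and EQ-Index estimate, its p-value and its effect size. That the listed terms force a constant difference follows from the SAP text alone. The size of the early weighting, and the shortfall from 0.34 to about 0.20 to 0.25 in the rising-difference example, rest on the assumed retention and correlation. The direction is the same in every dropout scenario examined. The rising and reversing profiles are illustrations; the documents predict neither. A reader might infer that the trial's HRQOL evidence as a whole, or its primary conclusions, are compromised. They are not: by-visit summaries exist, and the endpoint lies outside the alpha-controlled tests.

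**What to change.** In SAP 7.5.10, add treatment-by-visit to the fixed effects of the EQ-VAS and EQ-Index models, preferably with baseline-by-visit. Report the least squares mean difference and interval at each visit. Pre-specify either one visit or the equally weighted average over a stated window as the contrast to which the p-value and the 0.3 threshold apply.

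The cost is SAP wording and model code, with slightly wider intervals and a little more output. No new data, visits, subjects or alpha are needed. The by-visit t-tests, descriptives and plots can stay as they are.

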7.5.11 Health Care Resource Utilization

For this study the following health care resource utilization (HCRU) parameters collected during the study observation period will be summarized for the Safety population:

- Type of admission (hospital, intensive care unit (ICU), emergency unit)
- Descriptive statistics of number of hospital visits per subject
- Descriptive statistics of number of ICU visits per subject
- Descriptive statistics of number of emergency room (ER) visits per subject
- Total person-years of observation
- Total days of hospitalization
- Days of hospitalization per person-year
- Total days of ICU visit
- Days of ICU visit per person-year

Person-years total is calculated as the sum of [(end date of safety observation period – first dose date +1)/365.25] across all subjects in the given treatment group. To calculate the per person year value for a subject for a HCRU parameter, the numerator is the sum of the days or visits for that subject for the parameter; and the denominator is the applicable person-years of observation as defined.

7.6 Subgroups

The following subgroups based on baseline characteristics and stratification factors as reported by the investigator on the CRF will be explored for primary and secondary efficacy endpoints in the PITT and ITT populations. Forest plots will be provided for hazard ratios/odds ratio as applicable.

- Age category
 - <65 years
 - 65 to <75 years
 - 75 to <85 years
 - ≥85 years
- Sex
 - Male
 - Female

- Race
 - Asian
 - Black or African American
 - White
 - Rest of the races reported/Not Reported
- Geographic Regions (not mutually exclusive)
 - Asia
 - ❖ China + Hong Kong + Taiwan
 - Other Region (not Asia)
- ECOG Performance status at baseline:
 - 0
 - 1
- Etiology of disease per stratification factors per CRF:
 - HBV [with or without HCV]
 - HCV [without HBV]
 - Other
- Current etiology of disease (per cancer history CRF):
 - HBV [without HCV] (Yes)
 - HCV [without HBV] (Yes)
 - HBV and HCV (Yes)
 - Alcoholism (Yes)
 - Nonalcoholic Steatohepatitis (NASH) (Yes)
 - Other (Yes)
- Presence of extrahepatic spread of disease and/or macrovascular invasion (per cancer history CRF):
 - Yes
 - No
- Macrovascular invasion
 - Yes
 - No
- Extrahepatic disease
 - Yes
 - No
- Cirrhosis
 - Yes
 - No

- Lung metastasis per investigator
 - No
 - Yes
- Important visceral metastasis per investigator
 - No
 - Yes
- Number of organs at screening per investigator
 - 1
 - 2
 - ≥ 3
- AFP at baseline
 - <400 ng/mL
 - ≥ 400 ng/L
- Tumor PD-L1 status
 - Positive
 - Negative
 - Unknown

8 SAFETY SUMMARIES

Safety summaries will include all subjects in the Safety and P-Safety populations. Data to be included for Core and Crossover Periods and the treatment arm groupings for the summaries are described in Section 4.6. No formal statistical comparison between the experimental and control arms is planned.

Safety and tolerability will be assessed by the incidence of treatment emergent-adverse events (TEAEs), changes in laboratory parameters and vital signs from baseline, and ECOG PS.

An Independent Data Monitoring Committee (IDMC) will monitor safety of the subjects during the study on a regular basis. The committee will operate independently from the Sponsor and the clinical investigators.

The primary responsibility of the IDMC is to review the accumulating safety data on a regular and an ad hoc basis and make recommendations to the Sponsor regarding the continued conduct of the study. Safety data will be provided at regular intervals to the IDMC in the form of summary reports or data listings from the Sponsor or its designated representative.

Details regarding IDMC membership, schedule and format of meetings, format for presentation of data, access to interim data, method, and timing of providing interim reports to the IDMC, and other issues relevant to committee operations are described in the IDMC charter.

The IDMC members will use their expertise, experience, and judgment to evaluate the safety data from the trial and to recommend to the Sponsor whether the trial should continue or be stopped early for safety. No formal statistical rules recommending early stopping for safety are planned.

8.1 Adverse Events

Adverse event terms recorded on the CRF will be mapped to preferred terms and system organ class using the Medical Dictionary for Regulatory Activities (MedDRA). The severity of AEs will be measured by CTCAE ((Common Terminology Criteria for Adverse Events, version 5.0, 2017)) guidelines. The investigator will judge each event to be “not related” or “related” to study treatment. For subjects in the experimental arm, the investigator will judge each event’s relationship to study treatment, separately for cabozantinib and atezolizumab. However, in summarizing relationship of study treatment to adverse events in the experimental arm, relationship to either cabozantinib or atezolizumab will be considered as related to the experimental arm.

A TEAE is defined as any event with an onset date on or after the date of the first dose of study drug or any ongoing event on the date of the first dose of study drug that worsens in severity after the date of the first dose of study drug. In the Crossover phase, subjects who cross over to receive the experimental treatment, this definition will be with respect to the first dose of the experimental treatment received.

Unless otherwise specified, only TEAEs with an onset date (or date of increase in severity) through the end of the relevant safety observation period (see Section 4.6) will be tabulated in summary tables.

All deaths after informed consent, irrespective of when they occur, are classified as Grade 5 TEAEs. However, only those associated with an event starting after informed consent through 100 days after the date of the decision to discontinue the last component study treatment (or

starting at any time after informed consent and judged to be related to study treatment) required reporting as an SAE.

For the purpose of calculating treatment emergence and inclusion in summary tables, incomplete onset dates will be imputed as detailed in Appendix A. The calculations of percentages will be based on original unrounded values.

Summaries of AEs leading the changes in study treatment (e.g. leading to dose hold, reduction, modification, and/or discontinuation) will be based upon the fields for actions taken with each agent, collected on the AE CRF, e.g.

- Summaries of AEs leading to hold of oral treatment will include records where the “action taken” with cabozantinib or sorafenib = dose hold
- Summaries of AEs leading to hold of IV treatment will include records where the “action taken” with atezolizumab = dose delay
- Summaries of AEs leading to hold of **any** treatment will include records where the “action taken” with cabozantinib OR sorafenib is dose hold OR that for atezolizumab is dose delay
- Summaries of AEs leading to hold of **all** treatment will include records where the “action taken” with cabozantinib AND atezolizumab (for the combination regimen) or with sorafenib (for the control arm) = dose hold/delay as applicable

An overall summary of adverse events will be provided with the number and percent of subjects who experienced the following types of events during the standard safety observation period (unless otherwise noted as “at any time” or “during the extended safety observation periods” below) in each treatment arm:

- Subjects with a TEAE
- Subjects with a TEAE Related to Any Treatment Component
- Subjects with a Serious TEAE
- Subjects with a Serious TEAE during the extended safety observation periods
- Subjects with a Serious TEAE Related to Any Treatment Component at any time
- Subjects with a Worst-Grade 3 or 4 TEAE
- Subjects with a Worst-Grade 3 or 4 TEAE Related to Any Treatment Component
- Subjects with a Worst-Grade 4 TEAE
- Subjects with a Worst-Grade 4 TEAE Related to Any Treatment Component
- Subjects with a Grade 5 TEAE (death)

- Subjects with a Grade 5 TEAE (death) judged not to be causally related to disease under study
- Subjects with a Grade 5 TEAE Related to Any Treatment Component at any time (all treatment-related deaths)
- Subjects with a Grade 5 TEAE (death) Related to Any Treatment Component
- Subjects with a Grade 5 TEAE (death) during the extended safety observation period
- Subjects with a Grade 5 TEAE (death) judged not to be causally related to disease under study during the extended safety observation period
- Subjects with a Grade 5 TEAE (death) Related to Any Treatment Component during the extended safety observation period
- Subjects with a TEAE leading to Dose Modification
 - Modification of any treatment component
 - Modification of IV treatment
 - Modification of oral treatment
 - Modification of all treatment components
 - Modification of IV treatment only
- Modification of oral treatment only
- Subjects with a TEAE leading to Dose Reduction of oral treatment
- Subjects with a TEAE leading to Dose Hold of any treatment component
- Subjects with TEAE leading to Treatment Discontinuation at any time
 - Discontinuation of any treatment component
 - Discontinuation of IV treatment
 - Discontinuation of oral treatment
 - Discontinuation of all treatment components
 - Discontinuation of IV treatment only
 - Discontinuation of oral treatment only
 - TEAEs related to study treatment
 - Discontinuation of any treatment component
 - Discontinuation of IV treatment
 - Discontinuation of oral treatment
 - Discontinuation of all treatment components
 - Discontinuation of IV treatment only
 - Discontinuation of oral treatment only
 - TEAEs not related to any treatment component
 - TEAEs not causally related to disease under study
 - TEAEs causally related to disease under study

The following summaries of AEs will be provided:

TEAE included	Row-levels (sorted by)	Columns will Display	Safety Observation Period
Subject Incidence by SOC, Preferred Term and Severity			
All	SOC and PT (MedDRA standard)	Worst severity: All Grades, Grade 3/4, Grade 4, Grade 5	Standard
Related to any treatment component	SOC and PT (MedDRA standard)	Worst severity: All Grades, Grade 3/4, Grade 4, Grade 5	Standard
Serious	SOC and PT (MedDRA standard)	Worst severity: All Grades, Grade 3/4, Grade 4, Grade 5	Standard
Subject Incidence by Preferred Term and Severity			
All	PT (descending frequency of Any Grade)	Worst severity: All Grades, Grade 3/4, Grade 4, Grade 5	Standard
	PT (descending frequency of Grade 3/4)	Worst severity: All Grades, Grade 3/4, Grade 4, Grade 5	Standard
	PT (descending frequency of Any Grade)	Worst severity: All Grades, Grade 1, Grade 2, Grade 3, Grade 4, Grade 5	Standard
Related to any treatment component	PT (descending frequency of Any Grade)	Worst severity: All Grades, Grade 3/4, Grade 4, Grade 5	Standard
	PT (descending frequency of Grade 3/4)	Worst severity: All Grades, Grade 3/4, Grade 4, Grade 5	Standard
Serious	PT (descending frequency of Any Grade)	Worst severity: All Grades, Grade 3/4, Grade 4, Grade 5	Standard
	PT (descending frequency of Any Grade)	Worst severity: All Grades, Grade 3/4, Grade 4, Grade 5	Extended
Serious and Related to any treatment component	PT (descending frequency of Any Grade)	Worst severity: All Grades, Grade 3/4, Grade 4, Grade 5	Standard
	PT (descending frequency of Any Grade)	Worst severity: All Grades, Grade 3/4, Grade 4, Grade 5	At any time
Leading to Treatment Modification			
Leading to delay or hold of any treatment component	PT (descending frequency of Any Grade)	Worst severity: All Grades, Grade 3/4, Grade 4, Grade 5	Standard
	PT (descending frequency of Grade 3/4)	Worst severity: All Grades, Grade 3/4, Grade 4, Grade 5	Standard
Leading to delay or hold of all treatment components	PT (descending frequency of Any Grade)	Worst severity: All Grades, Grade 3/4, Grade 4, Grade 5	Standard
	PT (descending frequency of Grade 3/4)	Worst severity: All Grades, Grade 3/4, Grade 4, Grade 5	Standard
Leading to hold of oral study treatment	PT (descending frequency of Any Grade)	Worst severity: All Grades, Grade 3/4, Grade 4, Grade 5	Standard
	PT (descending frequency of Grade 3/4)	Worst severity: All Grades, Grade 3/4, Grade 4, Grade 5	Standard

TEAE included	Row-levels (sorted by)	Columns will Display	Safety Observation Period
Leading to IV treatment delay	PT (descending frequency of Any Grade)	Worst severity: All Grades, Grade 3/4, Grade 4, Grade 5	Standard
	PT (descending frequency of Grade 3/4)	Worst severity: All Grades, Grade 3/4, Grade 4, Grade 5	Standard
Leading to dose reduction of oral treatment	PT (descending frequency of Any Grade)	Worst severity: All Grades, Grade 3/4, Grade 4, Grade 5	Standard
	PT (descending frequency of Grade 3/4)	Worst severity: All Grades, Grade 3/4, Grade 4, Grade 5	Standard
Leading to dose modification of any treatment component	PT (descending frequency of Any Grade)	Worst severity: All Grades, Grade 3/4, Grade 4, Grade 5	Standard
	PT (descending frequency of Grade 3/4)	Worst severity: All Grades, Grade 3/4, Grade 4, Grade 5	Standard
Leading to dose modification of all treatment components	PT (descending frequency of Any Grade)	Worst severity: All Grades, Grade 3/4, Grade 4, Grade 5	Standard
	PT (descending frequency of Grade 3/4)	Worst severity: All Grades, Grade 3/4, Grade 4, Grade 5	Standard
Leading to dose modification of oral treatment	PT (descending frequency of Any Grade)	Worst severity: All Grades, Grade 3/4, Grade 4, Grade 5	Standard
	PT (descending frequency of Grade 3/4)	Worst severity: All Grades, Grade 3/4, Grade 4, Grade 5	Standard
Leading to dose modification of IV treatment	PT (descending frequency of Any Grade)	Worst severity: All Grades, Grade 3/4, Grade 4, Grade 5	Standard
	PT (descending frequency of Grade 3/4)	Worst severity: All Grades, Grade 3/4, Grade 4, Grade 5	Standard
Leading to Treatment Discontinuation			
Leading to discontinuation of any treatment component	PT (descending frequency of Any Grade)	Worst severity: All Grades, Grade 3/4, Grade 4, Grade 5	At any time
	PT (descending frequency of Grade 3/4)	Worst severity: All Grades, Grade 3/4, Grade 4, Grade 5	At any time
Leading to discontinuation of all study treatment components	PT (descending frequency of Any Grade)	Worst severity: All Grades, Grade 3/4, Grade 4, Grade 5	At any time
	PT (descending frequency of Grade 3/4)	Worst severity: All Grades, Grade 3/4, Grade 4, Grade 5	At any time
Leading to discontinuation of oral treatment	PT (descending frequency of Any Grade)	Worst severity: All Grades, Grade 3/4, Grade 4, Grade 5	At any time
Leading to discontinuation of IV treatment	PT (descending frequency of Any Grade)	Worst severity: All Grades, Grade 3/4, Grade 4, Grade 5	At any time
Leading to discontinuation of any treatment component and related to study treatment	PT (descending frequency of Any Grade)	Worst severity: All Grades, Grade 3/4, Grade 4, Grade 5	At any time
Leading to discontinuation of all treatment components and related to study treatment	PT (descending frequency of Any Grade)	Worst severity: All Grades, Grade 3/4, Grade 4, Grade 5	At any time

TEAE included	Row-levels (sorted by)	Columns will Display	Safety Observation Period
Leading to discontinuation of oral treatment and related to study treatment	PT (descending frequency of Any Grade)	Worst severity: All Grades, Grade 3/4, Grade 4, Grade 5	At any time
Leading to discontinuation of IV treatment and related to study treatment	PT (descending frequency of Any Grade)	Worst severity: All Grades, Grade 3/4, Grade 4, Grade 5	At any time
Leading to discontinuation of any treatment component and not related to study treatment and not causally related to disease under study	PT (descending frequency of Any Grade)	Worst severity: All Grades, Grade 3/4, Grade 4, Grade 5	At any time
Leading to discontinuation of all treatment components and not related to study treatment and not causally related to disease under study	PT (descending frequency of Any Grade)	Worst severity: All Grades, Grade 3/4, Grade 4, Grade 5	At any time
Leading to discontinuation of oral study treatment and not related to study treatment and not causally related to disease under study	PT (descending frequency of Any Grade)	Worst severity: All Grades, Grade 3/4, Grade 4, Grade 5	At any time
Leading to discontinuation of IV study treatment and not related to study treatment and not causally related to disease under study	PT (descending frequency of Any Grade)	Worst severity: All Grades, Grade 3/4, Grade 4, Grade 5	At any time
Leading to discontinuation of any treatment component and not related to study treatment and causally related to disease under study	PT (descending frequency of Any Grade)	Worst severity: All Grades, Grade 3/4, Grade 4, Grade 5	At any time
Leading to discontinuation of all treatment components and not related to study treatment and causally related to disease under study	PT (descending frequency of Any Grade)	Worst severity: All Grades, Grade 3/4, Grade 4, Grade 5	At any time
Leading to discontinuation of oral study treatment and not related to study treatment and causally related to disease under study	PT (descending frequency of Any Grade)	Worst severity: All Grades, Grade 3/4, Grade 4, Grade 5	At any time
Leading to discontinuation of IV study treatment and not related to study treatment and causally related to disease under study	PT (descending frequency of Any Grade)	Worst severity: All Grades, Grade 3/4, Grade 4, Grade 5	At any time
Subject Incidence of Grade 5 AEs with Odds ratio, Relative Risk and Risk Difference			
Grade 5	PT (descending frequency of difference)	All events	Standard
	PT (descending frequency of Grade 5)	Worst severity: Grade 5	Standard
	PT (descending frequency of Grade 5)	Worst severity: Grade 5	Extended
Grade 5 AEs judged not to be causally related to disease under study	PT (descending frequency of Grade 5)	Worst severity: Grade 5	Standard

TEAE included	Row-levels (sorted by)	Columns will Display	Safety Observation Period
	PT (descending frequency of Grade 5)	Worst severity: Grade 5	Extended
Grade 5 AE related to any treatment component	PT (descending frequency of Grade 5)	Worst severity: Grade 5	At any time
	PT (descending frequency of Grade 5)	Worst severity: Grade 5	Standard
	PT (descending frequency of Grade 5)	Worst severity: Grade 5	Extended
Subject Incidence by Special Criteria			
Events with an increase in the experimental arm of $\geq 5\%$ (All Grades) or $\geq 2\%$ (Grade 3/4)	SOC and PT (SOC per MedDRA standard, PT within SOC by decreasing difference between arms for All Grades)	Worst severity: All Grades, Grade 3/4, Grade 4, Grade 5	Standard
Non-serious adverse events of with an incidence of $\geq 5\%$ in any arm (Any Grade)	SOC and PT (SOC per MedDRA standard, PT within SOC by decreasing difference between arms for All Grades)	Worst severity: All Grades, Grade 3/4, Grade 4, Grade 5	Standard
All	PT (descending frequency of difference in percent between the two arms for All Grades)	Worst severity: All Grades, Grade 3/4, Grade 4, Grade 5	Standard
	PT (descending frequency of difference in percent between the two arms for Grade 3/4)	Worst severity: All Grades, Grade 3/4, Grade 4, Grade 5	Standard

In some of the above summaries classified by treatment exposure and relationship, the counts, and frequencies for the experimental arm (cabozantinib + atezolizumab) will be presented separately by individual treatment components as well as by combination.

The following data listings will also be provided with indicators for grade, relationship, seriousness, dose day of the event start/stop, days since last dose, actions taken with study treatment:

- All AEs
- Serious AEs
- All AEs that led to treatment discontinuation
- All AESI

